6.3 Criteria for Patient Discontinuation

Subjects may be discontinued from study treatment and assessments at any time. Specific reasons for discontinuing a subject for this study are:

- Voluntary discontinuation by the subject who is at any time free to discontinue his/her participation in the study, without prejudice to further treatment. In accordance with the Declaration of Helsinki, each subject is free to withdraw from the study at any time.
- Safety reason as judged by the Principal Investigator.
- Major protocol deviation.
- Incorrect enrolment i.e., the subject does not meet the required inclusion/exclusion criteria for the study.
- Subject lost to follow-up.
- Deterioration in the subject's condition, which in the opinion of the PI warrants study medication discontinuation (to be recorded as an AE).
- Subject non-compliance to study treatment and/or procedures, which in the opinion of the PI warrants study discontinuation.

6.4 Procedures for Discontinuation

6.4.1 Patient Discontinuation

Subjects who withdraw or are withdrawn from the study, will stop further treatment.

If possible, a final assessment (withdrawal visit) shall be made. The reason for discontinuation will be recorded. The investigator is obliged to follow up any significant adverse events until the outcome either is recovered or resolved, with sequela, fatal or unknown.

If a subject withdraw or are withdrawn from the study before start of treatment, it will be replaced by another individual that is found eligible according to the inclusion and exclusion criteria.

6.4.2 Trial Discontinuation

The whole trial may be discontinued at the discretion of the PI or the sponsor in the event of any of the following:

- Occurrence of AEs unknown to date in respect of their nature, severity and duration.
- Medical or ethical reasons affecting the continued performance of the trial.
- Difficulties in the recruitment of patients.
- Cancellation of investigational product development.

The sponsor and the PI will inform all investigators, the relevant Competent Authorities and Ethics Committees of the termination of the trial along with the reasons for such action. If the study is terminated early on grounds of safety, the Competent Authorities and Ethics Committees will be informed within 15 days.

6.5 Laboratory Tests

6.5.1 Blood samples

Serum: Drawn, collected and handled as routine samples and analyses by Dep. of Medical Biochemistry. Planned analyses: vitamin B12, folat, bilirubin, uric acid, C-reactive protein (CRP), sodium, potassium, creatinine, aspartate aminotransferase, ALAT, gamma-glutamyl transferase, lactat dehydrogenase, alkaline phosphatase, albumin, amylase, CK, and lipid profile. Additional analyses may be performed.

EDTA whole blood: Drawn, collected and handled as routine samples and analyses by Dep. of Medical Biochemistry and Dep. of Immunology. Planned analyses: hemoglobin, white blood cells differential count, thrombocytes, mean corpuscular hemoglobin, mean corpuscular volume, HbA1c, and CD4+, CD8+ T cell count, and genetic analysis for presence or absence of human leukocyte antigen variants HLA-A and HLA-DR1B. Additional analyses may be performed.

Plasma: Drawn, collected and handled as routine samples and analysis by Dep. of Medical Microbiology. Planned analysis: HIV RNA quantification. Additional analyses may be performed.

CPT tube, plasma and serum: Drawn, collected and handled by the Research and Development (R&D) section at Dep. of Infectious Diseases, OUH. Peripheral blood mononuclear cells (PBMC) will be isolated and frozen according to established laboratory protocols.(65) When inclusion of participants completed cells will be thawed according to established protocols and applied in functional *ex vivo* experiments and analyzed by flow cytometry. Additional analyses may be performed.

6.5.2 Colon biopsies

Forceps pinch biopsies will be collected at three different sites (terminal ileum, ascending colon and sigmoidum) during the colonoscopy. Each biopsy will be collected with a disposable biopsy forceps with a maximum insertion portion diameter of 3.3 mm (EndoJaw™, Olympus Medical Systems Corporation, Tokyo, Japan). At each site the following tissue specimens will be collected and handled in the following manner:

- Single biopsy swiftly weighted and washed in phosphate buffered saline (PBS) and then immersed in RNeasy Lysis Buffer (Qiagen). Incubated 24 hours in refrigerator (2-6°C), then frozen and stored at -20° until analyses. Four samples collected at each biopsy site. Collected and preserved for gut microbiota and gene expression analysis.
- Single biopsy swiftly washed in PBS and placed on a pre-cut approx. 15 x 3 mm carrot rod. Biopsy on carrot rod immersed in Tissue-Tek® O.C.T. Compound (Sakura Finetek Europe, Zoeterwoude, Netherlands), wrapped in aluminum foil, put in tube, and snap frozen in liquid nitrogen and stored in -70°C. One sample collected from each biopsy site. Collected and preserved for immunohistochemistry and *in situ* hybridization.
- Single biopsy swiftly washed in PBS and immediately immersed in 1.5 ml formaldehyde. Incubated 24 hours in refrigerator, then processed and embedded in paraffin. Collected and preserved for histopathology and immunohistochemistry.
- Twenty biopsies from each site pooled in 25 ml ice cold Hank's Balanced Salt Solution (HBSS). Washed twice in ice cold HBSS. Transferred to tube with ice cold RPMI culture medium with 10% fetal calf serum and 1% penicillin/streptomycin and brought to R&D section at Dep. of Infectious Diseases for collagenase digestion and filtering for isolation of single-cell suspension of lamina propria mononuclear cells (LPMC). Cells frozen according to the same established laboratory protocols as applied for PBMCs (See section 6.5.1). When inclusion of participants completed cells will be thawed according to established protocols and applied in functional *ex vivo* experiments and analyzed by flow cytometry.
- Single biopsy swiftly weighted and washed in PBS and put in clean tube and snap frozen in liquid nitrogen. Two samples collected at each biopsy site. Collected and preserved for HIV RNA quantification, Western blot and other protein and nucleic acid assays.

6.5.3 Stool samples

Stool will be sampled by the individual subjects immediately before he starts bowel emptying. Stool sample will be put in buffer-containing. *PSP® Spin Stool DNA sampling tube (Invitex) v01*. The sample tube will be collected by the investigator at colonoscopy visit and stored in -80°C for later nucleic acid-based assays for analysis of microbial composition and function.

7 ASSESSMENTS

7.1 Assessment of Efficacy

The primary objective of the intervention study is safety and is described in section 7.2.

The secondary objectives of the study are exploratory efficacy assessments. Efficacy of intervention and observed differences between groups will be evaluated by analyses of biologic material collected as described in section 6.5. Key *ex vivo* mucosal barrier assessments at weeks 0 and 8 are:

- Mucosa-adherent microbial composition
- Gene expression of mucosal tissue with validation of protein expression
- Frequency and activation status of LPMC subsets by flowcytometry
- Alterations in systemic T cells intracellular signaling
- Soluble markers of chronic inflammation and immune activation.

Efficacy assessments will be performed at the R&D section of the Department of Infectious Diseases, at the Norwegian PSC Research Centre, at the Department of Pathology, all OUH, and at the Biotechnology Centre at the UiO. These research labs have state of the art facilities for biomedical research and are committed to close scientific collaboration through the virtual K.G. Jebsen Inflammation Research Centre hosted by UiO

7.2 Safety and Tolerability Assessments

Safety will be monitored by the assessments described below as well as the collection of AEs at every visit. Significant findings that are present prior to the signing of informed consent must be included in the relevant medical history/ current medical condition page of the CRF. For details on AE collection and reporting, refer to Section 8.3.

For the assessment schedule refer to Flow chart in Section 6.1.

At inclusion (week 0) and at interventional product stop (week 8) patients will go through physical examination, vital signs evaluation, and blood samples for medical biochemistry analysis.

- Physical examination will include an examination of general appearance, skin, eyes, heart, abdomen, and peripheral lymph nodes.
- Vital signs include body temperature, blood pressure, pulse, and respiratory rate. Seated blood pressure and respiratory rate assessments will be performed after 2 min seated rest in a chair next to colonoscopy bench prior to colonoscopy.
- Medical biochemistry analysis consists of: Hemoglobin, white blood cells count, Thrombocytes, CRP, sodium, potassium, creatinine, ALAT, Bilirubin, Albumin, Amylase, and CK.

At weeks 1, 3, 5, and 7, participants will be telephoned and asked for side effects or adverse symptoms. Symptoms will be categorized as:

- General (fever, wellbeing/sense of illness, fatigue).
- Circulatory (palpitations, thoracic pain/discomfort, cold/painful extremities)
- Respiratory (shortness of breath, coughing, bronchial discharge)
- Dermal (rash, pruritus).
- Gastrointestinal (diarrhea, bloating, nausea, abdominal pain/discomfort).
- Other.

In case of side effects or adverse symptoms, participants will be called in for a visit for physical examination and vital signs and evaluation of need for discontinuation of study.

8 SAFETY MONITORING AND REPORTING

The investigator is responsible for the detection and documentation of events meeting the criteria and definition of an adverse event (AE) or serious adverse event (SAE). Each patient will be instructed to contact the investigator immediately should they manifest any signs or symptoms they perceive as serious.

The methods for collection of safety data are described below.

8.1 Definitions

8.1.1 Adverse Event (AE)

An AE is any untoward medical occurrence in a patient administered a pharmaceutical product and which does not necessarily have a causal relationship with this treatment.

An adverse event (AE) can therefore be any unfavorable and unintended sign (including an abnormal laboratory finding), symptom, or disease temporally associated with the use of a medicinal (investigational) product, whether or not related to the medicinal (investigational) product.

The term AE is used to include both serious and non-serious AEs.

If an abnormal laboratory value/vital sign are associated with clinical signs and symptoms, the sign/symptom should be reported as an AE and the associated laboratory result/vital sign should be considered additional information that must be collected on the relevant CRF.

8.1.2 Serious Adverse Event (SAE)

Any untoward medical occurrence that at any dose:

- Results in death
- Is immediately life-threatening
- Requires in-patient hospitalization or prolongation of existing hospitalization
- Results in persistent or significant disability or incapacity
- Is a congenital abnormality or birth defect
- Is an important medical event that may jeopardize the subject or may require medical intervention to prevent one of the outcomes listed above.

Medical and scientific judgment is to be exercised in deciding on the seriousness of a case. Important medical events may not be immediately life-threatening or result in death or hospitalization, but may jeopardize the subject or may require intervention to prevent one of the listed outcomes in the definitions above. In such situations, or in doubtful cases, the case should be considered as serious. Hospitalization for administrative reason (for observation or social reasons) is allowed at the investigator's discretion and will not qualify as serious unless there is an associated adverse event warranting hospitalization.

8.1.3 Suspected Unexpected Serious Adverse Reaction (SUSAR)

Adverse Reaction: all untoward and unintended responses to an investigational medicinal product related to any dose administered;

Unexpected Adverse Reaction: an adverse reaction, the nature or severity of which is not consistent with the applicable product information.

Suspected Unexpected Serious Adverse Reaction: SAE (see section 8.1.2) that is unexpected as defined in section 8.2 and possibly related to the investigational medicinal product(s).

8.2 Time Period for Reporting AE and SAE

For each patient the standard time period for collecting and recording AE and SAEs will begin at start of study treatment (week 0) and will continue 14 days following the last dose of study treatment, for each patient.

During the course of the study all AEs and SAEs will be proactively followed up for each patient; events should be followed up to resolution, unless the event is considered by the investigator to be unlikely to resolve due to the underlying disease. Every effort should be made to obtain a resolution for all events, even if the events continue after discontinuation/study completion.

8.3 Recording of Adverse Events

If the patient has experienced adverse event(s), the investigator will record the following information in the CRF:

- The nature of the event(s) will be described by the investigator in precise standard medical terminology (i.e. not necessarily the exact words used by the patient). ICD-10 diagnose applied if possible
- The duration of the event will be described in terms of event onset date and event ended data.
- The intensity of the adverse event will be graded on a 1-5 scale (1: mild; 2: moderate; 3: severe or medically significant; 4: life threatening; 5: death) according to Common Terminology Criteria for Adverse Events version 4.0 (CTCAE).(66)
- The Causal relationship of the event to the study medication will be assessed as one of the following:

Unrelated:

There is not a temporal relationship to investigational product administration (too early, or late, or investigational product not taken), or there is a reasonable causal relationship between non-investigational product, concurrent disease, or circumstance and the AE.

Unlikely:

There is a temporal relationship to investigational product administration, but there is not a reasonable causal relationship between the investigational product and the AE.

Possible:

There is reasonable causal relationship between the investigational product and the AE. De-challenge information is lacking or unclear.

Probable:

There is a reasonable causal relationship between the investigational product and the AE. The event responds to de-challenge. Re-challenge is not required.

Definite:

There is a reasonable causal relationship between the investigational product and the AE.

- Action taken, including withdrawal from the study.
- The outcome of the adverse event – whether the event is resolved or still ongoing.

It is important to distinguish between serious and severe AEs. Severity is a measure of intensity whereas seriousness is defined by the criteria in Section 8.1. An AE of severe intensity need not necessarily be considered serious. For example, nausea that persists for several hours may be considered severe nausea, but is not an SAE. On the other hand, a stroke that results in only a limited degree of disability may be considered a mild stroke, but would be an SAE.

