1.2 Background - Therapeutic Information

Probiotics are bacteria that may colonize the gut lumen and provide beneficial health effects, though the mechanisms of how they confer these effects are still largely unknown. (55, 56) We have already conducted a study of administering probiotics in treatment-naïve HIV patients and demonstrated reduction in immune activation in these patients.(57) Other small, preliminary studies have shown similar results.(58, 59) As argued in section 1.1, the increasing fraction of HIV patients on cART makes the relevance of adjuvant probiotic supplement higher in INR cART-treated patients than in treatment-naïve patients, but intervention studies with probiotics in INR HIV patients have not been performed.

Probiotics are generally well tolerated and smaller studies with other probiotic formulas of lower dose have been well tolerated in HIV-infected patients.(58-60) Still, cases of septicemia in young children and adults with compromised immunity have been observed.(61, 62) As our study population has impaired immunity we find it warranted to perform a phase I safety assessment of probiotic compounds before initiating larger efficacy studies in cART-treated INR HIV-infected patients.

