2.1 Primary Endpoint

i) Adverse effects; ii) Δ plasma viral load; and iii) Δ blood CD4 count.

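### The causality categories in section 8.3 are not mutually exclusive: a reasonable other cause is enough for Unrelated even when the product is also a reasonable cause, and Definite has no condition of its own

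*Combined protocol and SAP*

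**What the plan says.** Section 8.3 states that "The Causal relationship of the event to the study medication will be assessed as one of the following" and lists five categories.

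- *Unrelated* has two limbs joined by 'or'. The definition begins "There is not a temporal relationship to investigational product administration (too early, or late, or investigational product not taken), or there is a reasonable causal". The first limb is thus the absence of a temporal relationship. The second, in full, reads "or there is a reasonable causal relationship between non-investigational product, concurrent disease, or circumstance and the AE".
- *Unlikely* needs a temporal relationship and no reasonable causal relationship with the product.
- *Possible* needs a reasonable causal relationship with the product, and adds: "De-challenge information is lacking or unclear".
- *Probable* needs the same relationship, and adds: "The event responds to de-challenge. Re-challenge is not required".
- *Definite* repeats the sentence on a reasonable causal relationship and stops there.

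Relatedness is used again in section 8.1.3, where a SUSAR is an unexpected SAE that is possibly related to the product. Section 8.4.2 attaches deadlines of 7 days (fatal or life-threatening) and 15 days (all others).

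Section 2.1 gives the primary endpoint as "i) Adverse effects; ii) Δ plasma viral load; and iii) Δ blood CD4 count". Section 10.4 analyses the first of these under the name adverse events, as descriptive frequencies.

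**The concern.** If one category must be chosen, the definitions should lead two careful investigators to the same one. Here they need not.

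At the lower end, the second limb of *Unrelated* does not ask whether the product is also a reasonable cause. Septicaemia shows the difficulty. Section 1.2 says that "cases of septicemia in young children and adults with compromised immunity have been observed", and gives impaired immunity as a reason for doing a phase I study first. In an immunological non-responder the event has a reasonable link to the concurrent disease, which meets *Unrelated*. It may also have a reasonable link to a product of live bacteria, which meets *Possible* if de-challenge is unclear. Gastrointestinal symptoms, which section 7.2 solicits, raise the same problem. All treated patients take cART, and bowel emptying and colonoscopy with biopsies take place at weeks 0 and 8.

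At the upper end, a negative de-challenge would normally weaken the case for causality. Within the three product-related categories it leads to the strongest one. Negative de-challenge can be seen in routine follow-up, because patients who complete treatment stop at week 8 and section 8.2 collects events for 14 more days.

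The study has no control arm (section 3), so separating product effects from background rests largely on case-by-case judgement. An ambiguous scale weakens that judgement, and it can bear on which SAEs are handled as SUSARs.

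**Working it through.** **Inputs.** The five definitions in 8.3 are taken as printed and applied to four attributes of an event: temporal relationship (yes or no), reasonable link to another cause (yes or no), reasonable link to the product (yes or no), and de-challenge (lacking or unclear, positive, negative). That gives 2 × 2 × 2 × 3 = 24 combinations, 12 of them with a temporal relationship.

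**Combinations with a temporal relationship**

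| Product link reasonable | Other cause reasonable | De-challenge | Categories met |
|---|---|---|---|
| yes | no | lacking or unclear | Possible, Definite |
| yes | no | positive | Probable, Definite |
| yes | no | negative | Definite |
| yes | yes | lacking or unclear | Unrelated, Possible, Definite |
| yes | yes | positive | Unrelated, Probable, Definite |
| yes | yes | negative | Unrelated, Definite |
| no | no | any of the three | Unlikely |
| no | yes | any of the three | Unrelated, Unlikely |

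More than one category: 2 + 3 + 3 = 8 of 12. Exactly one: 1 + 3 = 4 of 12.

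**Combinations without a temporal relationship.** The six with no product link meet *Unrelated* only. The six with a product link also meet *Possible* or *Probable*, *Definite*, or both, which brings the total to 8 + 6 = 14 of 24. A reasonable product link without a temporal relationship is hardly realistic, so 8 of 12 is the fairer count. These are counts of combinations, not expected proportions of events.

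**Negative de-challenge.** With a temporal relationship there are four such combinations. *Definite* is the sole fit in one of them (product link, no other cause). With a product link and another cause, *Unrelated* is also open. Without a product link the event is *Unlikely*, or *Unrelated* and *Unlikely*.

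**Sensitivity to *Definite*.** Suppose *Definite* carries a further condition that the event does not meet, and remove it from the table. Two combinations with both links still meet *Unrelated* together with *Possible* or *Probable*, and three still meet *Unrelated* and *Unlikely*: 2 + 3 = 5 of 12. The combination of product link, no other cause and negative de-challenge then has no category at all.

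**The plan's own safety figures.** Section 10.1 gives Clopper-Pearson 95% intervals for SAEs in 20 patients.

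- 0/20: upper limit 1 − 0.025^(1/20) = 16.8%. The plan has (0%, 17%).
- 1/20: lower limit 1 − 0.975^(1/20) = 0.13%. The upper limit solves (1 − p)^20 + 20p(1 − p)^19 = 0.025, giving 24.9%. The plan has (0.1%, 25%).

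Both are reproduced. The numerator is the number of patients with an SAE, and relatedness does not enter it. Moving an SAE from *Unrelated* to *Possible* leaves it an SAE.

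**The case against.** The strongest reply is that little in the analysis depends on the scale. Section 10.4 presents adverse event frequencies with no causality filter, and section 8.1.1 counts an event whether or not it is related. This stands. A reader might infer from the term adverse effects in 2.1 that the rating decides what enters the primary endpoint, and that one re-rated SAE moves the result from 0/20 to 1/20. That would need a related-events definition which the plan does not contain. What remains is that 2.1 and 10.4 use different terms.

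Second, section 8.4.1 sends every SAE to the sponsor within 24 hours, and its report form to the ethics committee and the medicines agency. The sponsor makes its own evaluation of causality. This also stands, and it rules out the inference that an *Unrelated* rating hides an SAE. It is only a partial remedy. Section 8.4.1 sets no 7- or 15-day limit for sending the form, the protocol gives the sponsor no other causality scale, and non-serious events have no such safeguard. The SUSAR wording ("possibly related to the investigational medicinal product(s") is not tied to the 8.3 categories, so the scale can influence that decision but does not formally settle it.

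Third, an investigator may take persistence after stopping as grounds for finding no reasonable product link, and choose *Unlikely*. That is correct. A reader might infer that any persisting event must be *Definite*, or that unconnected events could be labelled so. The text does not support either, because all three upper categories first require a reasonable link to the product.

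Fourth, the remark under *Probable* that re-challenge is not required hints that *Definite* was meant to carry a further condition. Nothing marks a gap, but loss in reading the PDF cannot be fully excluded. The point about *Unrelated* does not depend on it.

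**Conclusion.** The concern holds for the definitions themselves. Section 8.3 asks for one category, yet 8 of the 12 combinations with a temporal relationship meet two or three; at least 5 of 12 would still do so if *Definite* had a condition of its own. The second limb of *Unrelated* overlaps with every other category. *Definite* as printed contains all of *Possible* and *Probable*. Among events judged reasonably related, it is the only one of the three product-related categories open to an event known to persist after stopping.

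The consequence is limited to the recorded relatedness of events in an uncontrolled safety study and, for unexpected SAEs, to possible ambiguity over the SUSAR test and its deadlines. No figure or planned analysis changes. The documents do not show how many events would be affected. It might be inferred that most events in this population have another reasonable cause, but the plan gives no frequency for this.

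The conclusion assumes a literal reading of 8.3 and, for the upper end only, that the printed text of *Definite* is complete. The point should be corrected, since safety is the primary objective and the correction is cheap.

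**What to change.** Reword 8.3 as a sequence in which each step applies only if the one before does not.

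- *Unrelated*: no temporal relationship.
- *Unlikely*: temporal relationship present, but no reasonable causal relationship with the product, including when another cause explains the event.
- *Possible*: temporal and reasonable causal relationship with the product, and either another cause is at least as reasonable, or de-challenge is lacking, unclear or negative.
- *Probable*: the same relationship, no other cause as reasonable, and positive de-challenge.
- *Definite*: as *Probable*, plus specific confirmation such as the product strain identified in a culture taken for care. An event that meets this is not rated *Probable*.

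Over the same 24 combinations, with 'other cause' now meaning one at least as reasonable, this gives 12 *Unrelated*, 6 *Unlikely*, 5 *Possible*, and 1 that is *Probable* or *Definite* according to confirmation: 12 + 6 + 5 + 1 = 24, each in one category.

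In 8.1.3, define possibly related as *Possible* or higher. Use one term in 2.1 and 10.4, keep all adverse events as the primary count, and show events rated *Possible* or higher alongside. The primary count should not be restricted to those events, because it would then depend on open-label ratings.

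The cost is protocol wording and one CRF page, with no extra visits, samples or patients. The downside is that slightly more events will be rated possibly related.
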